6.8. In Office Visit (1-Week)

Timely and complete follow-up visits will ensure the scientific integrity of the data is maintained and allow for continued oversight of subject safety.

The following study activities/data will be collected at the 1-week follow-up visit:

- Review of the subject diary for solicited events as defined in Section 7.4
- Assess recurrence of CDI
- Subject's weight
- Adverse event collection, including new onsets of obesity, metabolic syndrome, pre-diabetes, diabetes and/or autoimmune disorders
- Cdiff32 health-related quality of life questionnaire
- Changes to concomitant medications since the last visit
- Assess for protocol deviations
- For subjects who consented to the Optional Stool Sample collection, remind the subject to collect and ship a stool sample to Rebiotix

6.9. In Office Visit (4-Week)

The following study activities/data will be collected at the 4-week follow-up visit:

- Assess recurrence of CDI
- Subject's weight
- Adverse event collection, including new onsets of obesity, metabolic syndrome, pre-diabetes, diabetes and/or autoimmune disorders
- Cdiff32 health-related quality of life questionnaire
- Changes to concomitant medications since the last visit
- Assess for protocol deviations
- For subjects who consented to the Optional Stool Sample collection, remind the subject to collect and ship a stool sample to Rebiotix

6.10. In Office Visit (8-Week)

The 8-week follow-up visit is the primary efficacy endpoint timeline of the study. As such, every attempt should be made to ensure subjects understand the importance of this visit and are scheduled within the appropriate visit window.

The following study activities/data will be collected at the 8-week follow-up visit:

- Assess recurrence of CDI
- Subject's weight
- Adverse event collection, including new onsets of obesity, metabolic syndrome, pre-diabetes, diabetes and/or autoimmune disorders

- Changes to concomitant medications since the last visit
- Cdiff32 health-related quality of life questionnaire
- Verify employment status
- Assess changes in medical history, including Charlson Comorbidity Index variables. Worsening of conditions are to be captured as an adverse event with appropriate source documentation. An improvement in a condition may not have physician diagnosis or source documents to support improvement; subject self-reported improvement in a condition does not require medical documentation to support the improvement.
- Assess for protocol deviations
- For subjects who consented to the Optional Stool Sample collection, remind the subject to collect and ship a stool sample to Rebiotix

6.11. Telephone Assessments (Weeks 2, 3 and 6)

Qualified and trained site staff, as recorded on the Delegation of Authority Log, make the phone calls and may follow the script provided. All data collected are to be recorded and reported as required in Section 6.15. These phone calls must occur within the window specified in Table 6-1; phone calls out of window or missed phone calls are to be reported as protocol deviations.

The following study activities/data will be collected at the telephone assessment calls:

- Assess recurrence of CDI
- Adverse event collection, including new onsets of obesity, metabolic syndrome, pre-diabetes, diabetes and/or autoimmune disorders
- Changes to concomitant medications since the last visit
- Assess for protocol deviations

6.12. Telephone Assessments (3- and 6- Months)

Qualified and trained site staff, as recorded on the Delegation of Authority Log, make the phone calls and may follow the script provided. All data collected are to be recorded and reported as required in Section 6.15. These phone calls must occur within the window specified in Table 6-1; calls out of window or missed calls are to be reported as protocol deviations.

The following study activities/data will be collected at the telephone assessment calls:

- Assess recurrence of CDI
- Subject's weight, self-reported
- Adverse event collection, including new onsets of obesity, metabolic syndrome, pre-diabetes, diabetes and/or autoimmune disorders

- Changes to concomitant medications since the last visit
- Cdiff32 health-related quality of life questionnaire
- Verify employment status
- Assess changes in medical history, including Charlson Comorbidity Index variables. Worsening of conditions are to be captured as an adverse event with appropriate source documentation. An improvement in a condition may not have physician diagnosis or source documents to support improvement; subject self-reported improvement in a condition does not require medical documentation to support the improvement
- Assess for protocol deviations
- For subjects who consented to the Optional Stool Sample collection, remind the subject to collect and ship a stool sample to Rebiotix

The last phone call occurs 6 months after the date of the last administration of IP whether it was blinded or unblinded.

6.13. Unscheduled Possible Recurrence Visit

If CDI recurrence is suspected any time within 8 weeks of the last study enema due to documentation of three or more unformed/loose (i.e. Bristol Stool Scale type 6-7) stools within 24 or fewer consecutive hours for at least two consecutive days, possible treatment failure must be assessed. An in-office visit is required and the subject must provide a fresh stool sample to test for the presence of *C. difficile* toxin as defined by the protocol.

The following study activities/data will be collected at the Unscheduled Possible Recurrence visit:

- Collect fresh stool sample to send to the central laboratory for analysis
- Assess recurrence of CDI
- Vital signs: temperature, pulse, blood pressure, respiration
- Adverse event collection, including the new onsets of obesity, metabolic syndrome, pre-diabetes, diabetes and/or autoimmune disorders
- Changes to concomitant medications since last visit
- Cdiff32 health-related quality of life questionnaire
- Assess changes in medical history, including Charlson Comorbidity Index variables. Worsening of conditions are to be captured as an adverse event with appropriate source documentation. An improvement in a condition may not have physician diagnosis or source documents to support improvement; subject self-reported improvement in a condition does not require medical documentation to support the improvement.
- Assess for protocol deviations

- For subjects who consented to the Optional Stool Sample collection, remind the subject to collect and ship a stool sample to Rebiotix.

Treatment failure (CDI recurrence) is defined as:

- The presence of CDI diarrhea within 8 weeks of administration of a study enema, which includes a positive stool test for *C. difficile* toxin at the time of the diarrhea using the study required *C. difficile* testing algorithm.

[figure not shown]
To ensure consistency across clinical sites for the determination of study failure, the central laboratory will perform the required C. DIFF QUIK CHEK COMPLETE® Test (QCC Test) rapid enzyme immunoassay test for glutamate dehydrogenase (GDH) and toxins A and B.

In the case of suspected treatment failure where there is an immediate concern for subject safety, including the potential for serious adverse events, a C. DIFF QUIK CHEK COMPLETE® Test will be permitted to be conducted at the site or other laboratory known to the site **in addition to** sending a sample to the central laboratory for testing.

If the C. DIFF QUIK CHEK COMPLETE® Test is not available by the site or other laboratory, a testing algorithm that directly assesses the presence of *C. difficile* toxin for laboratory confirmation of recurrent CDI may also be used to test a sample, in addition to sending a sample to the central laboratory for testing.

[figure not shown]
Specifically, if the antigen and toxin are both positive per the QCC Test during the presence of diarrhea then the subject is considered a treatment failure.

Treatment Failure:

However, if the subject experiences diarrhea and the antigen and toxin are both negative per the QCC Test, then the subject is not considered a treatment failure as the presence of *C. difficile* was not established. The study investigator will need to determine the appropriate treatment for the subject as to avoid the possibility of serious adverse events.

Treatment Success:

Finally, if the antigen and toxin results per the QCC Test are inconclusive (one is positive and the other is negative), the stool sample will be sent to a central lab to perform a PCR test. If the PCR test is negative, the subject will not be considered a treatment failure as the presence of *C. difficile* was not established. If the PCR test is positive, then the subject will be considered a treatment failure.

Inconclusive Test, send sample for PCR testing:

Finally, if the QCC Test provides an invalid result such that the control line is not visible, the test will need to be repeated.

Invalid result, repeat testing immediately with new QCC Test:

6.14. Unblinded RBX2660

Subjects with a documented treatment failure meeting the protocol definition in the blinded portion of the study may be scheduled for administration of an unblinded RBX2660 enema. In order to receive the unblinded RBX2660 enema, a subject must have documentation of the following:

- Meeting all treatment failure criteria as defined by the protocol
- Compliance to the washout period (discontinuation of antibiotics for 24-72 hours prior to administration visit) is confirmed
- Negative urine-dipstick pregnancy test for subject of childbearing potential to confirm that they are not pregnant on the date of administration
- Unblinded enema administration is to occur within 21 calendar days of failure determination

While subjects may choose to receive and understand they are receiving an unblinded RBX2660 enema; neither they nor the study site will be unblinded to their original treatment.

If antibiotics are given to control symptoms, a 24-72hr washout period prior to administration of an unblinded RBX2660 enema is required, however the unblinded enema must still be administered within 21 calendar days of failure determination.

If a subject receives an unblinded RBX2660 enema, the follow-up requirements will restart from the day of administration of the unblinded RBX2660 enema according to the same schedule as required for the blinded portion of the study. This results in completion of a new subject diary from the day of unblinded RBX2660 enema administration until the day prior to the 1-week visit; in-office visits at 1-week (see Section 6.8), 4- week (see Section 6.9) and 8-week (see Section 6.10) as well as telephone calls at 2, 3 and 6 weeks (see Section 6.11) and at 3 and 6 months (see Section 6.12) after the unblinded RBX2660 treatment.

The study will be considered complete when all subjects have reached their 6-month follow-up after the last study enema received, including unblinded enemas, or have exited, whichever is earlier.

6.15. Study Exit

A Study Exit eCRF will be completed for each subject who is randomized. Data to be collected at this visit includes exit date and reason for study exit. This visit may occur in conjunction with the 6-month Follow-Up visit for subjects who complete the study and do not have ongoing adverse events.

The following information will be collected on the Study Exit eCRF:

- Exit date
- Reason for study exit
 - Completed Study
 - Screen Failure
 - Withdrawal by subject
 - Study Terminated by Sponsor
 - Investigator withdrawal
 - Adverse Event
 - Death
 - Lost to Follow-Up
 - Other: (specify)

Additional data will be collected when the following occur:

- Medication changes
- Adverse Events

6.16. Subject Withdrawal or Termination

A subject's study participation is considered complete once the 6-month telephone call is conducted after starting the last course of study drug or the subject exits the study, whichever comes first. A subject may withdraw at any time for any reason or be withdrawn from the study prematurely for the following reasons:

- Withdrawal of consent by subject
- Lost to follow-up
- Failure to comply to study requirements
- Termination of study by the sponsor
- Death
- Other (to be specified).

The reason for withdrawal is recorded on the Study Exit eCRF. In the event that a subject requests to withdraw from the study, every attempt should be made to have the subject return for an early withdrawal visit and to complete the required visit questionnaires prior to withdrawal.

For a subject who is suspected of being lost-to-follow-up, a minimum of three attempts must be made to contact subjects using two different contact methods (e.g., telephone, email, text, and letter); one attempt must be a registered postal letter or traceable courier notice (e.g., FedEx Express) to the subject's last known address. The contact attempts and methods are to be recorded on the Study Exit eCRF. The date the subject is regarded as lost to follow-up is the date of last actual encounter with the subject, such as the last phone call contact or visit.

Completion of a Study Exit eCRF is required for all randomized subjects when they exit the study regardless of reason, including completion of all study requirements, visits and assessments. Subjects who were randomized but were determined to be screen failures or otherwise exited prior to receiving a dose of the study drug should also be documented on a Study Exit eCRF.

7. Assessment of Safety

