3.8. Management of Treatment Failure

Following blinded treatment, subjects meeting the protocol definition of treatment failure may be scheduled for administration of an unblinded RBX2660 enema within 21 calendar days of failure determination. In order to receive the unblinded RBX2660 enema, the site must provide documentation of meeting all treatment failure criteria as defined by the protocol. If the subject has a subsequent treatment failure after the unblinded RBX2660 enema, the subject can be given another therapy as deemed appropriate by the treating investigator.

Without conclusive failure documentation, an unblinded RBX2660 will not be provided for administration.

Treatment failures are required to be entered in the study database shortly after determination of failure to allow for sponsor awareness and assurance that an unblinded RBX2660 can be provided if requested.

If antibiotics are given to control symptoms, a 24-72hr washout period prior to administration of an unblinded RBX2660 enema is required. If the subject will have the unblinded enema, it needs to be administered within 21 calendar days of failure

determination. The use of antibiotics prior to an unblinded RBX2660 enema is at the discretion of the investigator.

If a subject receives an unblinded RBX2660 enema, the follow-up requirements will restart from the day of the unblinded RBX2660 enema according to the same schedule as required for the blinded portion of the study. This results in completion of a new subject diary for up to 7 days after treatment; in-office visits at 1-, 4- and 8-weeks as well as telephone calls at 2-, 3- and 6- weeks and at 3 and 6 months after the last RBX2660 treatment.

Treatment failures who do not receive an unblinded RBX2660 enema will continue to follow their original schedule of assessments for the duration of the study based on the blinded study enema.

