5.4. Treatment Regimen

Randomization is to occur about 4-14 calendar days prior to the blinded study treatment to allow for notification to Rebiotix and shipment of product. Ultimately, the study treatment needs to be administered within 21 days of the Screening visit. Subjects are randomized to one of the following groups:

- Group A: Placebo
- Group B: RBX2660

Randomization will occur in a 2:1 fashion with two subjects randomized to receive RBX2660 for every one subject randomized to Placebo.

Once completed, assigned study treatment consists of a single blinded enema of either RBX2660 or Placebo as per the randomization assignment. Product is to only be administered by the authorized IP Administrator who must be a qualified and trained health care professional following the Instructions for Use and standard site procedures. Subjects are to remain at the site under supervision for at least one hour post-enema administration for vital sign assessment (temperature, heart rate, blood pressure, respiratory rate) and observation.

Subjects with a documented treatment failure following blinded treatment may be scheduled for administration of an unblinded RBX2660 enema. In order to receive an unblinded RBX2660 enema, a subject must have documentation of meeting all treatment failure criteria as defined by the protocol (Section 3.7).

If, in the opinion of the investigator, antibiotics are warranted for the control of CDI symptoms prior to receiving the unblinded RBX2660 enema, they can be administered but need to be stopped 24-72 hours before enema administration. The total time from a treatment failure (CDI recurrence) determination to administration of an unblinded enema is within 21 calendar days.

See Section 6 for the Schedule of Study Procedures and detailed description of the requirements.

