7.6.1. Initial Reports

All SAEs occurring from the time of informed consent until 6 months after administration of the last study enema of IP must be reported to Medpace Clinical Safety **within 24 hours** of the knowledge of the occurrence (this refers to any adverse event that meets any of the aforementioned serious criteria). All serious adverse events that the investigator considers related to study drug occurring after 6 months after administration of the last enema of IP must be reported to the Sponsor.

To report the SAE, complete the SAE form electronically in the electronic data capture (EDC) system for the study. When the form is completed, Medpace Safety personnel will be notified electronically and will retrieve the form. If the event meets serious criteria and it is not possible to access the EDC system, send an email to Medpace Safety at [contact] or call the Medpace SAE hotline (phone number listed below), and fax the completed paper SAE form to Medpace (fax number listed below) within 24 hours of awareness. When the EDC system becomes available, the SAE information must be entered within 24 hours of the system becoming available.

Safety Contact Information:
Medpace Clinical Safety

Medpace SAE hotline – USA:

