6.3.2 Modified Intent-to-Treat Population

For the Modified Intent-to-Treat (mITT) population, subjects will be analyzed according to the randomized treatment assignment despite any treatment misallocations.

Additionally, the mITT population will be defined as all randomized subjects who successfully received blinded treatment but excluding;

- subjects who withdrew prior to treatment;
- subjects in whom treatment was attempted but not completed and;
- subjects who discontinue from the study prior to evaluation of treatment failure/success for the primary endpoint if the reason for exit is not related to CDI symptoms. Reason for exit will be captured on the exit form to allow for identification of such subjects.

Examples of reasons unrelated to CDI symptoms may include;

- Withdrawal of consent
- Death unrelated to CDI

Subjects who were exited prior to the 8-week efficacy assessment due to CDI related symptoms will be counted as treatment failures even if documentation as required per the protocol is not on file for the treatment failure.

The mITT population will be used for the primary efficacy reporting purposes. The mITT population will also be used for secondary and exploratory endpoints evaluation. The analysis of the ITT and PP populations may also be provided in addition to the mITT for purposes of regulatory evaluation.

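### After the single blinded enema, non-compliance, an adverse event or an investigator decision should not by itself end follow-up, because an early exit for a non-CDI reason costs the primary analysis an outcome.

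*Protocol*

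**What the plan says.** - **Regimen.** Protocol 5.4: "assigned study treatment consists of a single blinded enema of either RBX2660 or Placebo as per the randomization assignment". The only further study treatment is optional and follows a documented failure. Protocol 3.8: "subjects meeting the protocol definition of treatment failure may be scheduled for administration of an unblinded RBX2660 enema within 21 calendar days of failure determination".
- **Withdrawal.** Protocol 6.16: "A subject may withdraw at any time for any reason or be withdrawn from the study prematurely for the following reasons". The list includes "Failure to comply to study requirements" and an open category for other reasons. No item is confined to the period before the enema. Participation is complete at exit. An early withdrawal visit is asked for only when the subject requests to leave.
- **Exit form.** Protocol 6.15 lists "Investigator withdrawal" and "Adverse Event". Neither is named in 6.16. Conversely, non-compliance is named in 6.16 but has no entry of its own on the form.
- **Primary set.** SAP 6.3.2 excludes from mITT "subjects who discontinue from the study prior to evaluation of treatment failure/success for the primary endpoint" when the exit reason, taken from the exit form, is unrelated to CDI symptoms. CDI-related exits before week 8 stay in as failures.
- **Secondary endpoint.** In the responder comparison of SAP 7.6.2.1, a week-8 success who leaves before 6 months is counted as a sustained failure. The time-to-event analysis in the same section censors such a subject.
- **Safety.** Protocol 7.1 follows adverse events until resolution or exit. Protocol 7.6.1 says "All SAEs occurring from the time of informed consent until 6 months after administration of the last study enema of IP must be reported". Protocol 7.6.2 (SAEs) and 7.8 (events causally related to product or procedure) require follow-up to resolution or stabilisation, without reference to exit.

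**The concern.** In a trial with continuing dosing, withdrawal for non-compliance or an adverse event can at least limit exposure. Here the blinded dose has already been given, so the exit only stops the scheduled visits and calls.

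These exits happen after dosing and may be related to outcome. Take a subject who uses an antibiotic restricted through week 8. If exited as non-compliant, the subject leaves the mITT denominator; if exited for CDI symptoms, the same subject is a failure. The site-recorded reason makes the difference. The endpoint committee adjudicates success and failure, but no text gives it review of exit reasons. Protocol 3.13 concedes that the product administrator may guess the assignment, and it asks subjects to disregard colour and odour. Equal exit patterns in the two arms therefore cannot be assumed.

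At stake are avoidable missing primary outcomes, a possible bias in the mITT success rates, false failures in the secondary endpoint, and the loss of scheduled safety contacts.

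**Working it through.** **1. The plan's own sample size.** Inputs from Protocol 8.1: 69% against 47% success, 2:1 allocation, 90% power, nominal 2.5% type I error (read as one-sided). The placebo-arm size is

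n = [0.47×0.53 + (0.69×0.31)/2] × (1.960 + 1.282)² / 0.22² = 77.3, so 78.

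With 156 on RBX2660 the total is 234, within 3% of the stated 240. At 160 against 80 the approximate power is 91.0%. The loss allowance is also consistent: 270 × 0.9 = 243. The sample size is not in question. These are fixed-sample frequentist checks and do not reproduce the Bayesian primary analysis.

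**2. What happens to a treated subject who exits.**

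| Exit | Primary mITT | ITT (sensitivity) | 6-month response, mITT |
|---|---|---|---|
| Before week-8 evaluation, CDI-related | kept as failure | failure | failure |
| Before week-8 evaluation, not CDI-related | dropped | failure | not in set |
| After week-8 success, before 6 months | kept as success | success | failure |

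In the second row neither set uses the outcome that the subject would have had: mITT omits it and ITT imputes failure. The per-protocol set excludes these exits in the same way as mITT.

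**3. Shift in one arm's mITT success rate.** Let p be the true success rate, f the share exiting for these reasons and s the true success rate among them. Then

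mITT rate = (p − f·s) / (1 − f).

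The documents give neither f nor s. Assume f = 5% and s = 20-40%:

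- RBX2660, p = 0.69: s = 0.4 gives 0.67/0.95 = 0.705 (+1.5 points); s = 0.2 gives 0.68/0.95 = 0.716 (+2.6 points).
- Placebo, p = 0.47: s = 0.4 gives 0.45/0.95 = 0.474 (+0.4 points); s = 0.2 gives 0.46/0.95 = 0.484 (+1.4 points).

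**4. Effect on the treatment difference (true value 22 points).** Exits from RBX2660 alone raise it by 1.5-2.6 points. Exits from placebo alone lower it by 0.4-1.4 points. Equal exits with equal s in both arms give 0.22/0.95 = 23.2 points, a rise of 1.2.

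**5. No true effect.** Take 47% in both arms, exits from RBX2660 only, and 0-20% success among them (assumptions). The false difference is:

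- 2% exits: 0.6-1.0 points
- 5% exits: 1.4-2.5 points
- 10% exits: 3.0-5.2 points

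It is zero if exits are unrelated to outcome (s = 0.47).

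**6. Precision.** Approximate power is 93.8% if all 270 are followed. With 10% excluded from both arms (243 evaluable) it is 91.3%. With the same 10% counted as failures (62.1% against 42.3%) it is 87.3%. Ten percent of 270 is 27 subjects; if a quarter to a half of those losses were avoidable exits (assumption), 7-14 primary outcomes would be lost.

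**The case against.** The case against has several sound parts.

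- **Safety.** A reader might infer that exit ends safety follow-up. The documents do not support that. SAE reporting to 6 months, SAE follow-up and follow-up of related events are not tied to exit, and exited subjects stay in the safety population. What ends is scheduled contact and general adverse event follow-up, which leaves Protocol 7.1 to be reconciled with 7.6.1, 7.6.2 and 7.8.
- **Primary set.** A reader might also infer that any such exit removes the subject from mITT. It does so only before the primary evaluation and for a non-CDI reason. The SAP appendix (Primary Analysis Population) says, without a condition on reason, that mITT dropouts are failures. That does not restore the subjects whom 6.3.2 excludes from the set, and the two texts should be worded alike.
- **The antibiotic example.** Loose stools treated with antibiotics may well be recorded as CDI symptoms, and a suspected failure without a central laboratory result goes to the blinded endpoint committee. This covers suspected recurrences, but not an exit recorded simply as non-compliance.
- **Authority to withdraw.** Section 6.15 is a list of form fields. Non-compliance also has a natural use before dosing, nothing obliges a site to withdraw a treated subject, and missed contacts are already reported as deviations. Even so, 6.16 permits the withdrawal after dosing and no text keeps the subject in outcome follow-up.
- **Exit reasons.** Deleting adverse event as an exit reason would undercut the SAP 7.7.1 tables of events resulting in withdrawal and could push such exits into consent withdrawal, which mITT also drops. This stands, and the reason fields should be kept.
- **Safeguards.** The ITT analysis and the 30 extra subjects help with sensitivity and power, but neither recovers an observed outcome.

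**Conclusion.** The concern holds in a limited form. After the enema, withdrawal for non-compliance, an adverse event or an investigator decision saves no blinded exposure. Before the primary evaluation, and for a non-CDI reason, it removes an outcome from the deciding analysis. After a week-8 success, it creates a failure in the secondary responder comparison.

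The size and direction of any bias are unknown. The per-arm shifts of about 1.5-2.6 points (RBX2660) and 0.4-1.4 points (placebo) rest on an assumed 5% exit share and an assumed 20-40% success rate among those exits. A reader might infer that the rule favours RBX2660. The documents do not show this, because the net effect depends on which arm loses whom, and it is nil if exits are unrelated to outcome under no true effect. Nor is this a sample-size error: the stated 240 reproduces, and approximate power stays above 90% with 10% excluded.

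The point is a preventable source of missing primary data that a minor amendment would reduce.

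**What to change.** - In Protocol 6.16, state that after the blinded enema non-compliance, an adverse event or an investigator decision is not by itself a reason to end follow-up. Record it as a deviation or an adverse event, and keep the reason fields that the planned withdrawal tables need.
- Keep the subject on the scheduled contacts to week 8 and 6 months unless the subject withdraws consent, dies or is lost to follow-up, or the sponsor ends the study. The observed outcome is then used in mITT. Protocol 3.8 already does this for failures who decline the unblinded enema.
- Align the reason lists in 6.15 and 6.16.
- Reconcile Protocol 7.1 with 7.6.1, 7.6.2 and 7.8, and SAP 6.3.2 with the appendix text on mITT dropouts.
- Reconcile the new text with SAP 4.1, under which a subject who pursues non-study treatment after a CDI episode is exited.

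The change alters no dose or clinical rule. It leaves the mITT rule itself in place, so genuine consent withdrawals before week 8 would still be dropped. The cost is a minor protocol amendment, matching edits to the exit form and SAP, and some extra site effort to follow these subjects.
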